#### 6.4.1.4 Procedure for Reporting Serious Adverse Events, Adverse Events of Special Interest

#### **Serious Adverse Events**

In the event of any new SAE occurring during the reporting period, the Investigator must immediately (within a maximum 24 hours after becoming aware of the event) inform the IND Office and/or Merck/EMD Serono using the SAE Report Form following specific completion instructions.

In exceptional circumstances, a SAE (or follow-up information) may be reported by telephone; in these cases SAE Report Form must be provided immediately thereafter.

Reporting procedures and timelines are the same for any new information on a previously reported SAE (= follow-up).

Relevant pages from the eCRF (Prometheus) may be provided in parallel (for example, medical history, concomitant drugs). Additional documents may be provided by the Investigator, if available (for example, laboratory results, hospital report, and autopsy report). In all cases, the information provided on the SAE Report Form must be consistent with the data about the event recorded in the eCRF (Prometheus).

The Investigator must respond to any request for follow-up information (for example, additional information, outcome final evaluation, other records where needed) or to any question the IND Office and/or Merck/EMD Serono may have on the AE within the same timelines as those noted above for initial reports. This is necessary to ensure a prompt assessment of the event by the IND Office and/or Merck/EMD Serono and (as applicable) to allow the IND Office to meet strict regulatory timelines associated with expedited safety reporting obligations.

#### **Adverse Events of Special Interest**

In the event of a non-serious Grade  $\geq$  3 AESI, the Investigator must report the AESI using the eSAE database within 5 days, and the logs should be provided to Merck/EMD Serono every 3 months. Serious AESIs have to be reported in an expedited manner as SAEs within 24 hours as outlined above, and reported to EMD Safety. For Grade 1 and Grade 2 non-serious AESIs, results from the eSAE database should be forwarded to Merck/EMD Serono every 3 months.

Safety Report to Health Authorities, Independent Ethics Committees / Institutional Review Boards and Investigators

The IND Office will send appropriate safety notifications to Health Authorities in accordance with applicable laws and regulations.

The Investigator must comply with any applicable site-specific requirements related to the reporting of SAEs (particularly deaths) involving trial subjects to the IEC / IRB that approved the trial.

In accordance with ICH GCP guidelines, Merck/EMD Serono will inform the Investigator of "findings that could adversely affect the safety of subjects, impact the conduct of the trial, or alter the IEC's / IRB's approval / favorable opinion to continue the trial." In particular and in line with respective regulations, Merck/EMD Serono will inform the Investigator of AEs that are both serious and unexpected and are considered to be related to the administered product (suspected unexpected serious adverse reactions [SUSARs]). The Investigator should place copies of Safety Reports in the Investigator Site File. National regulations with regard to Safety Report notifications to Investigators will be taken into account.

When specifically required by regulations and guidelines, Merck/EMD Serono will provide appropriate Safety Reports directly to the concerned lead IEC / IRB and will maintain records of these notifications. When direct reporting is not clearly defined by national or site-specific regulations, the Investigator will be responsible for promptly notifying the concerned IEC / IRB of any Safety Reports provided by Merck/EMD Serono and of filing copies of all related correspondence in the Investigator Site File.

## 6.4.1.5 Monitoring of Subjects with Adverse Events

Adverse events are recorded and assessed continuously throughout the trial (see Section 6.4.1.3) and are assessed for final outcome at the End of Treatment visit. After the End of Treatment visit only AEs that are deemed attributable to trial drug by the Investigator should be documented until the Safety Follow-up visit.

All SAEs ongoing at the 28-Day Safety Follow-up visit must be monitored and followed up by the Investigator until stabilization or until the outcome is known, unless the subject is documented as "lost to follow-up". In addition, all trial drug related SAEs occurring after 28-Day Safety Follow-up visit and ongoing at the Safety Follow-up visit must be followed up in the same manner.

Reasonable attempts to obtain this information must be made and documented. It is also the responsibility of the Investigator to ensure that any necessary additional therapeutic measures and follow-up procedures are performed.

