#### 6.4.1.3 Definition of the Adverse Event Reporting Period

The AE reporting period for safety surveillance from the first protocol intervention to 90 days after last study drug administration and continues through the trial's 28-Day Safety Follow-up visit, defined as 28 days ( $\pm$  5 days) after last trial drug administration. After the 28-Day Safety Followup visit only AEs that are deemed attributable to trial drug by the Investigator should be documented until the Safety Follow-up visit, defined as 28 days (+/- 7 days) after the last trial drug administration.

Any SAE assessed as related to M7824 must be reported whenever it occurs, irrespective of the time elapsed since the last administration of M7824.

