#### 6.4.4 Vital Signs, Physical Examinations, and Other Assessments

The ECOG PS will be assessed at Screening and at subsequent visits as indicated in the Schedules of Assessments (**Tables 1-3**) and documented in the eCRF (Prometheus).

Body weight will be measured at Screening and at subsequent visits as indicated in the Schedules of Assessments (**Tables 1-3**) and documented in the eCRF (Prometheus). Body height will be measured at screening only.

A physical examination will be conducted at Screening and at subsequent visits as indicated in the Schedules of Assessments (**Tables 1-3**) and documented in the eCRF (detailed description in Section 6.1). Any abnormalities arising or worsening after the signing of the ICF should be

documented in the eCRF (Prometheus) Adverse Event section (see Section 6.4.1). Abnormal findings are to be reassessed at subsequent visits.

Physical examination should include a dermatological examination. If abnormal skin findings are observed, the patient should be referred to a dermatologist for biopsy of suspicious lesions.

An ophthalmology examination including slit lamp evaluation inclusive of the anterior segment and with visual acuity should be conducted at Screening. At subsequent visits, eye signs and symptoms should be checked. If there are any clinically relevant findings then an appropriate ophthalmology examination including slit lamp evaluation inclusive of the anterior segment and with visual acuity should be obtained within 2 days.

Digital 12-lead EKGs will be recorded as a single recording at the screening visit. Subsequent EKGs will likewise be obtained as single recordings.

All newly diagnosed or worsening conditions, signs and symptoms observed since Screening, whether related to trial treatment or not, are to be reported as AEs.

For female subjects of childbearing potential, serum  $\beta$ -HCG pregnancy test will be carried out during the Screening phase. A urine  $\beta$ -HCG test may be performed prior to schedule on treatment assessments. Results of the most recent pregnancy test should be available prior to the next dosing of IMP. Subjects who are postmenopausal (age-related amenorrhea  $\geq 12$  consecutive months and if needed FSH > 40 mIU/mL [in the postmenopausal range] as outlined in Section 6.1.1), or who have undergone hysterectomy or bilateral oophorectomy are exempt from pregnancy testing. If necessary to confirm postmenopausal status, an FSH will be drawn at Screening.

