## 7.5.3 Analysis of Endpoints

## 7.5.3.1 Secondary Endpoints

The secondary endpoints of PFS (cohorts A-C and B) and DFS (cohort D) according to iRECIST 1.1 and OS time will be presented using the Kaplan-Meier method. PFS will be measured in months from the date of first administration of M7824 to the date of documented progression by RECIST 1.1 or death by any cause, whichever is earlier. For Cohort D, DFS will be measured in months from the date of documented recurrence or development of distant metastasis by iRECIST 1.1 criteria. Median PFS and DFS and 95% confidence intervals will be estimated using the Kaplan-Meier method.

OS will be measured in months from the date of first administration of M7824 to the date of death by any cause. Median OS with 95% confidence interval will be estimated using the Kaplan-Meier method. Severity of AEs will be graded using the NCI-CTCAE v4.03 toxicity grading scale. Safety will be assessed by descriptive statistics and summarized in tabular format. This data will be separated based on organ class, immune-relation, severity and relation to M7824.

Adverse events (serious and non-serious) will be considered treatment emergent adverse events when emerging during the on-treatment period defined as the time from first trial drug administration to the last drug administration date + 30 days or the earliest date of subsequent anticancer drug therapy minus 1 day, whichever occurs first, unless otherwise stated. All premature terminations will be summarized by primary reason for treatment withdrawal.

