## 7.5.3.3 Adverse Events

Severity of AEs will be graded using the NCI-CTCAE v4.03 toxicity grading scale. Safety will be assessed by descriptive statistics and summarized in tabular format. This data will be separated based on organ class, immune-relation, severity and relation to M7824.

Adverse events (serious and non-serious) will be considered treatment emergent adverse events when emerging in the on-treatment period defined as the time from the first trial drug administration to the last drug administration date + 30 days or the earliest date of subsequent anticancer drug therapy minus 1 day, whichever occurs first, unless otherwise stated. All premature terminations will be summarized by primary reason for treatment withdrawal.

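### The sections disagree on when all-cause AE recording stops, and under 6.4.1.5 non-serious unrelated AEs can go unrecorded before the 30-day treatment-emergent window closes

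*Combined protocol and SAP*

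**What the plan says.** **Analysis window.** Section 7.5.3.1 states: "Adverse events (serious and non-serious) will be considered treatment emergent adverse events when emerging during the on-treatment period". Section 7.5.3.3 gives the limits of that period as follows: "first trial drug administration to the last drug administration date + 30 days or the earliest date of subsequent anticancer drug therapy minus 1 day". The earlier of the two end dates applies. Attribution plays no part in the definition. On the tables, 7.5.3.3 adds: "This data will be separated based on organ class, immune-relation, severity and relation to M7824".

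**Recording rules.** Three different rules appear:

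- Section 6.4.1.5, repeated in the footnotes to Tables 1, 2 and 3: "After the End of Treatment visit only AEs that are deemed attributable to trial drug by the Investigator should be documented". Under 6.1.3.1 the End of Treatment visit takes place 0 to 7 days after the decision to stop.
- Section 6.4.1.3, the definition of the reporting period: "After the 28-Day Safety Followup visit only AEs that are deemed attributable to trial drug by the Investigator should be documented". The same section also gives a reporting period of 90 days after the last dose.
- Section 6.4.4: new or worsening conditions since screening, "whether related to trial treatment or not, are to be reported as AEs".

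**SAEs.** Section 6.4.1.1.1 captures SAEs to 90 days after the last dose and requires them to be reported whatever their attribution.

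**The concern.** A table of treatment-emergent AEs by relation is readable only if related and unrelated events are collected over the same days. Under 6.4.1.5 and the schedule footnotes they are not. Before the End of Treatment visit all AEs are recorded; after it, a non-serious event enters the record only if the investigator attributes it to the drug. The analysis window takes no account of that change.

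The error has one direction. Let R be the related events in the window, U the unrelated events, and u the unrelated events left unrecorded. The table shows R + U − u events instead of R + U, and a related share of R/(R + U − u), which exceeds R/(R + U) whenever R and u are above zero. Section 7.5.1 evaluates data as observed without imputation, so an undocumented event is analysed as no event.

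Sites also cannot follow all three rules at once. Practice may differ between patients, and the tables would not show which rule had been applied.

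**Working it through.** The plan gives no figure to reproduce. The check compares the day on which all-cause recording stops with the day on which the window closes, both counted from the last dose.

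**Inputs.** Window end: day 30 (7.5.3.1, 7.5.3.3). End of Treatment visit: 0 to 7 days after the decision to stop (6.1.3.1). 28-day visit: day 28 ± 5 (6.1.4.1 and 6.4.1.3; 6.4.1.3 also gives ± 7). Dosing interval: 14 days. The delay from last dose to the decision to stop is not given in the documents. It is an assumption, shown over a range.

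**Formula.** Gap = max(0, 30 − day on which all-cause recording stops).

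**Cut at the End of Treatment visit (6.4.1.5 and footnotes):**

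| Decision to stop, days after last dose (assumed) | Visit day | Gap, days |
|---|---|---|
| 0 | 0 to 7 | 23 to 30 |
| 7 | 7 to 14 | 16 to 23 |
| 14 (next planned dose) | 14 to 21 | 9 to 16 |
| 21 | 21 to 28 | 2 to 9 |
| 28 | 28 to 35 | 0 to 2 |

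**Cut at the 28-day visit (6.4.1.3):** visit on day 28, gap 30 − 28 = 2 days. With ± 5 days the visit falls on day 23 to 33, so the gap is 7 to 0 days. With ± 7 days it falls on day 21 to 35, so the gap is 9 to 0 days.

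**Share of the window affected.** Window length = (doses − 1) × 14 + 30 days. For a gap of 9 to 16 days:

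- 4 doses: 42 + 30 = 72 days; 9/72 = 12.5% to 16/72 = 22%.
- 6 doses: 70 + 30 = 100 days; 9% to 16%.
- 26 doses: 350 + 30 = 380 days; 9/380 = 2.4% to 16/380 = 4.2%.

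These are shares of days, not of events. All the gaps assume that no new anticancer drug therapy starts before day 30; if it does, the window closes earlier and the gap shrinks or disappears.

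**SAEs:** capture to day 90 covers day 30, so the gap for unrelated SAEs is 0 under either rule.

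**The case against.** The strongest reply is that 6.4.1.3 governs. Section 6.4 names it as the place where the reporting period is defined, and 6.4.1.5 itself cites it. Section 6.4.1.2 asks for complete data on all AEs in that period, and 6.1.4.1 lists AEs at the 28-day visit with no attribution filter. On that reading the gap is about 2 days.

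This stands in part. A reader might infer that the plan necessarily loses unrelated events over the last weeks. The documents do not support that, because the loss follows from one of several conflicting rules. But 6.4.1.3 does not settle the matter. It restricts recording after the 28-day visit until a safety visit that is also set at 28 days, which leaves almost no interval, and it names 90 days as well. Sections 6.1.3.1 and 6.1.4.1 allow the 28-day assessments to be done at End of Treatment for subjects who cannot return. The schedules that sites work from carry the End of Treatment rule.

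Four further limits are sound:

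- **Not all unrelated events are exposed.** Unrelated SAEs are captured to day 90. Section 6.4.1.1 makes clinical Grade 4 and 5 AEs SAEs, and 6.4.1.1.3 has suspected immune-related events and infusion reactions reported as events of special interest. What remains is mainly non-serious events outside those categories.
- **A large loss among the sickest patients is not shown.** Section 6.4.1.1.2 already excludes most signs and symptoms of progression from AE reporting.
- **The safety endpoint and stopping rule do not count these events.** Section 7.3.2 lists treatment-related AEs, and 7.6 counts only related AEs of Grade 3 or higher. A reader might argue that an unrecorded event cannot later be re-attributed and so could alter the interim count. That is possible for a non-serious Grade 3 event, but it is indirect, and the documents give no basis for sizing it.
- **Cohort B has a separate limit.** The recording grid in 6.4.1.1 lists unrelated and unlikely AEs only from Grade 3 in Phase II, so low-grade unrelated AEs may be absent throughout treatment.

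**Conclusion.** The point holds as a contradiction between recording rules with a one-directional consequence for some tables. Where 6.4.1.5 and the footnotes are applied, the all-cause and unrelated treatment-emergent AE tables are too low for non-serious events, and the related share is too high. The size depends on an assumed delay between the last dose and the decision to stop: 9 to 16 days of missing all-cause recording if that decision falls at the next planned dose, with 0 to 30 days possible. Under 6.4.1.3 with a day-28 visit it is about 2 days. Early stoppers lose a larger share of their window than long-treated patients, but no number of lost events can be derived from the documents. It should be corrected because safety and tolerability is a secondary objective in every cohort (3.2) and unrecorded events are hard to recover later. It does not undermine the listed safety endpoint or the toxicity monitoring.

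**What to change.** Reconcile 6.4.1.3, 6.4.1.5, 6.4.4 and the footnotes to Tables 1-3 so that AEs are documented regardless of attribution through day 30 after the last dose, or to the day before new anticancer drug therapy if earlier. Anchor the rule to day 30 and not to the 28 ± 5 day visit, which can fall on day 23 and leave 7 days uncovered. Section 6.4.1.3 needs rewording too, since its 28-day and 90-day statements do not agree.

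If that is not wanted, end the all-cause window in 7.5.3.1 and 7.5.3.3 where all-cause recording ends, and label the tables accordingly.

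For Cohort B, state that the tables follow the recording grid in 6.4.1.1, with unrelated and unlikely AEs only from Grade 3. Changing the End of Treatment wording alone would not make those tables all-cause.

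The cost is a wording change and a few more non-serious AE entries. AEs are already reviewed at the 28-day visit (6.1.4.1); when that visit falls before day 30, the remaining days need a brief later check.

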### 6.4.2 Pregnancy and In Utero Drug Exposure

Only pregnancies considered by the Investigator to be related to trial treatment (for example, resulting from a drug interaction with a contraceptive medication) are considered to be AEs; however, all pregnancies with an estimated conception date during the period defined in Section 6.4.1.3 must be recorded by convention in the AE page / section of the eCRF (Prometheus). The same rule applies to pregnancies in female subjects and to pregnancies in female partners of male subjects. The Investigator must also notify the IND Office in an expedited manner of any pregnancy using the Paper Pregnancy Report Form, which must be transmitted according to the same timelines as described for SAE reporting in Section 6.4.1.4.

Investigators must actively follow up, document and report on the outcome of all these pregnancies, even if the subjects are withdrawn from the trial.

The Investigator must notify the IND Office of these outcomes using the Pregnancy Report Form. If an abnormal outcome occurs, the SAE Report Form will be used if the subject sustains an event and the Parent-Child / Fetus Adverse Event Report Form if the child / fetus sustains an event.

Any abnormal outcome must be reported in an expedited manner as described in Section 6.4.1.4, while normal outcomes must be reported within 45 days after delivery.

In the event of a pregnancy in a subject occurring during the course of the trial, the subject must be discontinued from trial medication immediately. The IND Office must be notified without delay and the subject must be followed as mentioned above.

#### 6.4.3 Clinical Laboratory Assessments

It is essential that the IND Office be provided with a list of laboratory normal ranges before shipment of IMP. Any change in laboratory normal ranges during the trial will additionally be forwarded to the IND Office.

Blood samples will be taken from non-fasted subjects. All routine laboratory analyses will be performed at a laboratory facility local to the investigational site and relevant results must be drawn and checked before administration of M7824. The report of the results must be retained as a part of the subject's medical record or source documents. Complete blood count and full serum chemistry must be checked within 72 hours prior to each dose administration.

ANA, RF, T4, TSH, and urinalysis will be assessed at the time points defined in the Schedules of Assessments (**Tables 1-3**).

If confirmation of a subject's postmenopausal status is necessary, a FSH level will also be performed at Screening, see Section 6.1.1.

Full Chemistry	Hematology	
Albumin	Absolute lymphocyte count	
Alkaline phosphatase	Absolute neutrophil count	
Alanine aminotransferase	Hematocrit	
Amylase +	Hemoglobin	
Aspartate aminotransferase	Platelet count	
Bicarbonate	RBC count	
Blood urea nitrogen / total urea	White blood cell count and differential count	
Calcium	Red blood cell morphology**	
Chloride	Reticulocytes	
	Mean corpuscular hemoglobin	
Creatine kinase	Mean corpuscular volume	
Creatinine	Mean corpuscular hemoglobin concentration	
C-reactive protein		
Glucose		
Lactate dehydrogenase		
Lipase +		
Phosphorus / phosphates		
Magnesium	Basic Urinalysis (dipstick, including macroscopic appearance,	
Potassium	bilirubin, blood, color, glucose, ketones, leukocyte esterase	
Sodium	Full urinalysis (dipstick plus microscopic evaluation) to be performed only at the Screening and 28-Day Safety Follow-up	
Total bilirubin / direct bilirubin/ indirect bilirubin*	visits and a basic urinalysis prior to Day 1 of every cycle.	
Total protein		
Uric acid		
	ANA***, RF***, TSH, and T4	

#### Table 7: Required Laboratory Panel Tests

ACTH=adrenocorticotropic hormone; ANA=antinuclear antibody; IMP=Investigational Medicinal Product; PCR = polymerase chain reaction; RF=rheumatoid factor; TSH=thyroid-stimulating hormone; T4=free thyroxine.

\*\* Only in case of anemia onset assessed as related to study treatment

+Only day 1 of every cycle

**\*\*\***Only at pre-screening evaluation (see schedule of assessments)

a If hepatitis B surface antigen positive and hepatitis B core antibody positive, then reflex to quantitative HBV DNA (PCR); if hepatitis B core antibody positive alone, then reflex to quantitative hepatitis B DNA (PCR); if hepatitis C antibody positive, then reflex to quantitative hepatitis C RNA (PCR).

If a subject has a clinically significant abnormal laboratory test value that is not present at Baseline, the test will be repeated weekly and the subject will be followed until the test value has returned to the normal range or the Investigator has determined that the abnormality is chronic or stable.

For **pharmacokinetic assessment of M7824**, a blood sample should be collected prior to infusion of M7824 and following completion (within 30 minutes) of infusion of M7824 (doses 1 and 3), prior to dose 2, and prior to dose 6/end of treatment visit (whichever of these two comes first). Samples should be processed as follows:

- 1. Collect 3.5 mL of blood in an SST tube with silica clot activator and polymer gel.
- 2. Gently invert the tube 5 times to mix the clot activator with the blood.
- 3. Allow blood to clot for 30 minutes at room temperature in a vertical position.
- 4. After allowing clot to form, centrifuge the tube for 15 minutes at 1100-1300x g at 25°C. If refrigerated centrifuge is available, set the temperature at 25°C in order to prevent heating during centrifugation and to optimize flow of the barrier material. Flow may be impeded if chilled before or during centrifugation.
- 5. Carefully collect and aliquot the serum equally into 2 separate Micronics tubes.
- 6. Place the tubes immediately into the freezer in an upright position at -80°C.
- 7. Samples will be analyzed as a batch with EMD Serono at a later date.

